250 mg lebrikizumab SC injection	1 injection of 250 mg lebrikizumab 1 injection of placebo	1 injection of 250 mg lebrikizumab 1 injection of placebo	1 injection of lebrikizumab 250 mg Q2W
Placebo SC injection	2 injections of 250 mg lebrikizumab	2 injections of 250 mg lebrikizumab	1 injection of lebrikizumab 250 mg Q2W

Abbreviations: Q2W = every 2 weeks; SC = subcutaneous.

Patients who do not achieve EASI 50 for at least 2 consecutive visits assessed at Weeks 24, 28, 32, 36, 40, 44, or 48 will be discontinued from the study.

Safety, laboratory, and clinical assessments will be performed as specified in the Schedule of Assessment (SoA) ([Table 1](#)).

Efficacy will be measured as follows:

- Clinical signs: EASI score, IGA score, BSA affected by AD lesions
- Clinical signs and patient reported symptoms: SCORAD score
- AD Patient Reported Symptoms: Pruritus NRS, Sleep-loss scale, Skin Pain NRS, Patient-Oriented Eczema Measure (POEM).
- Quality of life (QoL) and impact of disease: Dermatology Life Quality Index (DLQI) or Children's Dermatology Life Quality Index (CDLQI), DLQI-Relevant (DLQI-R), World Health Organisation-Five Well-Being Index (WHO-5), Recap of Atopic Eczema (RECAP), and Treatment Satisfaction Questionnaire for Medication-9 items (TSQM-9).

Safety will be assessed by monitoring AEs, serum chemistry, haematology and urinalysis laboratory test results, physical examination results, and vital signs.

Blood samples will be collected at Baseline and Week 16 to assess biomarkers, [CCI](#) [REDACTED]

[figure not shown]
Photographs of lesions will be obtained from a subset of patients participating in this study as outlined in the Photography Manual. The photographs should not only include the lesion(s) but also a greater body area and the upper and lower body, including the face, limbs, and hands (back and palms).

Patients completing the study treatment and patients who terminate early will undergo a SFU visit approximately 18 weeks after the last study drug injection. For patients who complete the study, the last dose of treatment will occur at Week 50. Therefore, the SFU visit will occur at Week 68.

The EOS is defined as the date of the last visit of the last patient in the study shown in the SoA ([Table 1](#)).

The trial design is represented schematically in [Figure 1](#).

Figure 1 Lebrikizumab Phase 3 Study Design Schematic

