7.2 Trial Rationale

7.2.1 Rationale for Trial Design

The design for the Induction and Maintenance Periods for this trial is similar to the design used in the other lebrikizumab phase 3 trials and is commonly used in AD trials.

This study will enrol adult and adolescent patients with moderate-to-severe AD whose AD is not adequately controlled with cyclosporine or for whom cyclosporine is not medically advisable and therefore for whom a systemic treatment such as lebrikizumab may therefore be appropriate.

The Induction Period of the study has a double-blind, placebo-controlled design to guarantee an unbiased assessment of the primary and secondary efficacy variables at Week 16 in comparison with placebo. A duration of 16 weeks of placebo treatment is deemed acceptable in this patient population, also considering that all patients will receive background TCS therapy at a dosage that can be adapted based on the patient's needs.

Starting from Week 16, all patients will receive the active drug. From Week 20 onward, the study will have an open-label design to give patients randomised to placebo the opportunity to receive lebrikizumab treatment and to assess long-term efficacy and safety of lebrikizumab while adapting or discontinuing concomitant TCS therapy. Discontinuing patients who do not achieve or maintain a clinical response during the Maintenance Period will ensure that patients are not unnecessarily given treatment that is not effective.

TCS are the first-line anti-inflammatory treatment, even for patients treated with systemic therapies. For this reason, this study will assess the efficacy of lebrikizumab in combination with background mid or low-potency TCS, forced at Baseline and during the Induction Period, and used as determined appropriate by the Investigator from Week 16 onward.

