8.3.2 Study Drug Discontinuation

Study drug must be permanently discontinued for patients who experience the following:

- AE, laboratory abnormality or intercurrent illness for which continued treatment, in the opinion of the Investigator, would affect assessments of clinical status or patient safety to a significant degree
- TEAEs that are clinically significant, deemed persistent, and that, in the opinion of the Investigator, continued treatment would affect assessments of clinical status or patient safety to a significant degree
- Unacceptable toxicity
- Pregnancy
- Use of systemic rescue medication as outlined in [Section 9.9.3](#)
- No response to treatment as specified in [Section 7.1](#)

Patients who permanently discontinue study drug will be requested to:

- perform all the end-of-treatment visit assessments at their next scheduled site visit
- perform a SFU visit approximately 18 weeks after the last study drug injection, except for patients receiving systemic rescue medication as per [Section 9.9.4](#).

All information, including the reason for permanent discontinuation of study drug will be recorded in the patient's study records and in the eCRF.

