All inferential analyses of the primary and key secondary efficacy endpoints, including multiple imputation approaches will be conducted during the Induction Period only (eg, up to and including Week 16). During the Maintenance Period, only descriptive analyses will be performed for efficacy. The handling of estimands as detailed above will also only apply up to and including Week 16. After this point, data will only be analysed as observed.

In addition, to support efficacy analyses, a summary of the incidence of the ICEs at each visit up to Week 16 will be presented.

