13.2.5.2. Table Conventions

- Units will be included where available
- For categorical parameters, all categories will be presented in the table, even if n=0 for all treatment groups in a given category. For example, the frequency distribution for symptom severity would appear as:

Severity Rating	N
severe	0
moderate	8
mild	3

Where percentages are presented in these tables, zero percentages will not be presented and so counts of 0 will be presented as 0 and not as 0 (0%).

- An Unknown or Missing category will be added to each parameter for which information is not available for 1 or more patients
- Unless otherwise specified, the estimated mean and median for a set of values will be printed out to 1 more significant digit than the original values, and standard deviations will be printed out to 2 more significant digits than the original values. The minimum and maximum will report the same significant digits as the original values. For example, systolic blood pressure will be presented as follows:

N	XX
Mean	XXX.X
Std Dev	X.XX
Median	XXX.X
Minimum	XXX
Maximum	XXX

- P-values will be output in the format: '0.xxx', where xxx is the value rounded to 3 decimal places. Every p-value less than 0.001 will be presented as <0.001. If the p-value are less than 0.0001, then present as <0.0001. If the p-value is returned as >0.999, then present as >0.999
- Percentage values will be printed to one decimal place, in parentheses with no spaces, one space after the count (e.g., 7 (12.8%), 13 (5.4%)). Unless otherwise noted, for all percentages, the number of patients in the analysis set for the treatment group who have an observation will be the denominator. Percentages after zero counts will not be displayed and percentages equating to 100% will be presented as 100%, without decimal places
- Tabular display of data for medical history, prior/concomitant medications, and all tabular displays of adverse event data will be presented by the body system, treatment class, or SOC with the

This document is confidential.

highest occurrence in the active treatment group in decreasing order, assuming all terms are coded. Within the body system, drug class and SOC, medical history (by preferred term), drugs (by ATC1 code), and adverse events (by preferred term) will be displayed in decreasing order. If incidence for more than 1 term is identical, they will then be sorted alphabetically. Missing descriptive statistics or p-values which cannot be estimated will be reported as '-'

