
- The percentage of patients will normally be calculated as a proportion of the number of patients assessed in the relevant treatment group (or overall) for the analysis set presented. However, careful consideration is required in many instances due to the complicated nature of selecting the denominator, usually the appropriate number of patients exposed. Details will be described in footnotes or programming notes, as necessary
- For categorical summaries (number and percentage of patients) where a patient can be included in more than one category, a footnote or programming note will be added describing whether the patient is included in the summary statistics for all relevant categories or just 1 category as well as the selection criteria
- Where a category with a subheading (such as system organ class) has to be split over more than one page, output the subheading followed by '(cont)' at the top of each subsequent page. The overall summary statistics for the subheading should only be output on the first relevant page

13.2.5.3. *Listing Conventions*

- Listings will be sorted for presentation in order of treatment groups as above, patient number, visit/collection day, and visit/collection time
- Missing data will be represented on patient listings as either a hyphen ('-') with a corresponding footnote ('- = unknown or not evaluated'), or as 'N/A', with the footnote 'N/A = not applicable', whichever is appropriate
- Dates will be printed in SAS DATE9.format ('DD_MMM_YYYY': 01JUL2000). Missing portions of dates will be represented on patient listings as dashes (–JUL2000). Dates that are missing because they are not applicable for the patient will be output as 'N/A', unless otherwise specified
- All observed time values will be presented using a 24-hour clock HH:MM or HH:MM:SS format (e.g., 11:26:45, or 11:26). Time will only be reported if it was measured as part of the study
- Units will be included where available

13.2.5.4. *Figure Conventions*

- Unless otherwise specified, for all figures, study visits will be displayed on the X-axis and endpoint (e.g., treatment mean change from Baseline) values will be displayed on the Y-axis

13.2.6. *Footnotes*

- A solid line spanning the margins will separate the body of the data display from the footnotes.
- All footnotes will be left justified with single-line spacing immediately below the solid line underneath the data display

This document is confidential.

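### As-observed by-week EASI response late in Maintenance can be raised, because patients removed for EASI 50 non-response also leave the default denominator

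*SAP*

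**What the plan says.** - **Removal rule.** Protocol 7.1 provides that "Patients who do not achieve EASI 50 for at least 2 consecutive visits assessed at Weeks 24, 28, 32, 36, 40, 44, or 48" leave the study. Protocol 8.3.2 lists the same non-response as a reason to stop study drug permanently. Protocol 7.2.1 shows that this is intended: "Discontinuing patients who do not achieve or maintain a clinical response during the Maintenance Period" is meant to spare patients a treatment that is not working for them.
- **Last assessment.** Under Protocol 8.3.2 such patients are asked to "perform all the end-of-treatment visit assessments at their next scheduled site visit". The schedule of assessments has a single combined column, W52/EoT. SAP 7.4 organises data by scheduled time point, but its window table lists only Weeks 2 to 14.
- **Data handling.** SAP 9.3 and Protocol 11.8.1.1 both limit the estimand handling to Week 16 and then state: "After this point, data will only be analysed as observed". SAP 7.3 imputes nothing else.
- **Denominator.** SAP 13.2.5.2 says that, unless noted otherwise, "the number of patients in the analysis set for the treatment group who have an observation will be the denominator". It repeats this with a qualifier: "The percentage of patients will normally be calculated as a proportion of the number of patients assessed in the relevant treatment group". It adds that "careful consideration is required in many instances due to the complicated nature of selecting the denominator" and leaves details to footnotes or programming notes. SAP 9.7 says only that the Maintenance analyses are descriptive and on the FAS.
- **Endpoint.** EASI 50, 75 and 90 by week from Week 16 to Week 52 are secondary endpoints in both documents (Protocol Section 6, Table 3; SAP 3).

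**The concern.** Each rule is reasonable alone, but together they act as a filter. A patient removed under Protocol 7.1 has just been recorded at two visits as a non-responder for EASI 50, and hence for EASI 75 and EASI 90. From then on the patient is in neither numerator nor denominator. The by-week percentage can climb although no patient improves.

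Up to Week 16 the plan does the opposite: under the main estimand, discontinuation for lack of efficacy is set to baseline, which is a non-response (SAP 6.1.1).

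At stake is how the Week 16 to 52 response curve is read. Protocol 7.2.4 wants it to show whether response is maintained. A curve that rises through attrition of non-responders looks like continued improvement.

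**Working it through.** **Inputs.** The documents give neither a removal share nor a Maintenance response rate, so there is no stated figure to reproduce. Two planning numbers from SAP 4.3 serve as illustration only: 208 patients in the lebrikizumab arm, and 55% EASI 75, which is a Week 16 assumption. The removal share x is assumed to lie between 2% and 20%.

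**Step 1: the identity.** Let R be the rate with removed patients counted as non-responders, and x = removed/(observed + removed). Removal leaves the responder count unchanged and shrinks the denominator by (1−x):

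as-observed rate = R/(1−x); gap = R·x/(1−x).

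At R = 55%:

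| x | As observed | Gap (points) |
|---|---|---|
| 2% | 0.55/0.98 = 56.1% | 1.1 |
| 5% | 0.55/0.95 = 57.9% | 2.9 |
| 10% | 0.55/0.90 = 61.1% | 6.1 |
| 20% | 0.55/0.80 = 68.8% | 13.8 |

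The gap is proportional to R, so it is largest for EASI 50. At x = 10%, assumed rates of 75, 55 and 35% for EASI 50, 75 and 90 read 83.3, 61.1 and 38.9%.

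**Step 2: if removed patients could have recovered.** Suppose a share r of them would have responded later. The rate had they stayed is R + r·x. With r = 20% and R = 55%, the as-observed rate is still too high by 0.7, 1.9, 4.1 and 9.8 points at x = 2, 5, 10 and 20%. The gap closes only if r = R/(1−x), that is, if patients with two consecutive EASI 50 failures would have responded at 56 to 69%.

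**Step 3: when it starts.** The earliest trigger is Weeks 24 and 28. The end-of-treatment assessment follows at the next site visit, normally Week 32 because Week 30 may be remote. Tabulated at its actual week, it keeps the patient in the Week 32 denominator, so the effect begins at Week 36.

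**Step 4: an EASI 75 time profile.** Assume 208 patients, 114 EASI 75 responders throughout, no other dropout, and 4 non-responders removed after each of Weeks 28, 32, 36, 40, 44 and 48 (24 in total). All attend the end-of-treatment visit.

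| Week | Tabulated at actual week |
|---|---|
| 28 | 114/208 = 54.8% |
| 32 | 114/208 = 54.8% |
| 36 | 114/204 = 55.9% |
| 40 | 114/200 = 57.0% |
| 44 | 114/196 = 58.2% |
| 48 | 114/192 = 59.4% |
| 52 | 114/188 = 60.6% |

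With all removed patients kept as non-responders, every row is 54.8%. With 1 removal per visit instead of 4, Week 52 reads 114/203 = 56.2%.

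**Step 5: the same patients tabulated under W52/EoT.** Week 48 reads 114/188 = 60.6%. At Week 52 all 24 reappear and the rate is 114/208 = 54.8%, or 114/196 = 58.2% if half attend. The effect is then largely offset at Week 52, but the curve drops from Week 48 although no patient worsened.

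**The case against.** **The analysis is legitimate and descriptive.** Protocol and SAP agree on as-observed reporting. From Week 16 all patients receive lebrikizumab, so there is no placebo contrast and no test. This stands: the plan contains no contradiction. The point concerns what the printed percentage will be taken to mean.

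**Readers can already recover a rate.** SAP 13.2.4 puts group N in the column header, and SAP 13.2.5.2 adds that "An Unknown or Missing category will be added to each parameter for which information is not available for 1 or more patients". Responders over N therefore gives a full non-responder rate, and discontinuation reasons (SAP 8.1) and by-patient listings (SAP 9.4) show why patients left. This stands too. But that rate also counts unrelated dropouts as failures, and the printed percentage is still the as-observed one.

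**The denominator is only a default.** True; a footnote could change it. No such exception for these endpoints appears in either document.

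**The size is assumed.** Also true. With few removals the effect is small.

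**The time profile is stylised.** It can hold for EASI 75 status only. If EASI 50 status were also fixed, every persistent non-responder would go after Week 28 in one step. Staggered removal needs patients who fall below EASI 50 later.

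**Tempting stronger readings.** A reader might infer that the effect begins at Week 32 and that the example reaches 114/184 = 62.0% at Week 52. That needs end-of-treatment assessments to be left out of the table. Protocol 8.3.2 places them at a scheduled site visit, so patients removed after Week 48 would normally be seen at Week 52 itself. A reader might also infer that IGA, itch, skin pain and DLQI response must rise in the same way. They may, but failing EASI 50 does not by itself make a patient a non-responder on those measures.

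**Conclusion.** The point holds for EASI 50, 75 and 90 by week in the Maintenance Period. If any patients are removed under the rule, the default table prints a rate 1/(1−x) times the rate that keeps them as non-responders. The direction follows from the stated rules; the size does not. It rests on an unstated removal share: from 1.1 points at x = 2% to 13.8 points at x = 20%, for an assumed 55% rate. With early end-of-treatment data at their actual week, the effect starts at Week 36, and the EASI 75 example reads 60.6% instead of 54.8% at Week 52. With those data under W52/EoT, the effect is largely offset at Week 52 at the price of an artificial drop from Week 48. The SAP does not say which applies.

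A reader might infer that the trial's efficacy conclusion is affected. The documents do not support that. Success rests on the Week 16 primary endpoint alone (SAP 7.9), and Week 16 results and power are unaffected.

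**What to change.** In SAP 9.7, before the Week 52 database lock:

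1. Keep the as-observed table, labelled as response among patients still on study, with the number observed and the cumulative number removed by week and arm.
2. Add one descriptive by-week table for EASI 50, 75 and 90, Weeks 16 to 52, by randomised arm, among FAS patients who entered Maintenance. Count patients discontinued under the EASI 50 rule or for lack of efficacy as non-responders at all later weeks. The weekly denominator is patients observed plus patients so counted, each once. Show other dropouts and missed visits in separate rows and do not count them as failures.
3. State that early end-of-treatment assessments are tabulated at their actual week, and as Week 52 only if they fall in that week's window.

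The stopping rule is not changed. The cost is one extra descriptive table from data already collected, and lower reported long-term rates by the gaps in the first table above. The added rate may understate the response that removed patients would have reached had they continued, which is a reason to print both tables.

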9.4. Analysis of all Other Secondary and Other Efficacy Endpoint

The main and second estimands as described in Section 6.1.2 will be analysed by means of a mixed effect model for repeated measures (MMRM), including the Baseline value as a covariate, and adjusting by the factors of country, age (adolescents/adults), Baseline severity of disease (IGA=3/IGA=4), previous exposure to dupilumab (yes/no, when the overall population is analysed) and visit and treatment-visit interaction. A restricted maximum likelihood method will be specified, along with an unstructured covariance matrix. Estimates of the LS Means for each of the 2 treatment groups at each visit up to and including Week 16, along with the difference between treatments in LS Means, 2-sided 95% CI and p-value for the difference will be presented.

Example SAS syntax is as follows:

CCI

This document is confidential.

CCI

For all continuous secondary efficacy endpoints, in case of non-convergence, the country factor will be removed from the model.

Time-to-event (TTE) endpoints will be analysed on the second estimand for continuous endpoints using Kaplan-Meier survival analysis methods. If available, for descriptive purposes, the estimate of the median time-to-event (in weeks) and the 2-sided 95% CI will be presented. A comparison of the survival distribution curves for the 2 treatment groups will be made by means of the log-rank test. The Cox proportional hazards model will be used to estimate the hazard ratio and its 95% CI of lebrikizumab compared with placebo at the respective time point. The main Cox proportional hazards model will include treatment group, with country, age, Baseline disease severity and previous exposure to dupilumab (when the overall population is analysed) as factors. The proportional hazard assumption will be evaluated on all factors (ie, treatment and stratification factors) by graphical inspection of the Schoenfeld residuals and by Grambsch and Therneau test as well. Country may be removed from the model as appropriate, similar to the other analyses of efficacy. Because of the fact that the Induction and Maintenance Periods will be reported separately, TTE endpoints will be analysed at 2 separate time points: initially up to and including Week 16, and then separately for the whole study, incorporating both the Induction and Maintenance Periods.

All binary other secondary and other efficacy endpoints will be analysed using the same methodology as described for the primary efficacy endpoint using only the main estimand. Sensitivity analyses based on the PPS population will not be conducted for these endpoints.

All efficacy variables for the Maintenance/Extension Period will be analysed by means of descriptive statistics presented by treatment group as randomised during the Induction Period.

Additionally, all secondary and CCI efficacy endpoints for the secondary objective will be presented in by-patient listings.

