9.6.2 Randomisation

Patients who meet all criteria for enrolment will be assigned a randomisation number through the IWRS, in accordance with the randomisation code generated by the authorised personnel at PPD. Once a randomisation number is allocated to a patient, it may not be assigned to another patient even if the former discontinued the study.

Eligible patients will be enrolled and randomised 2:1 on Study Day 1 to either 250 mg lebrikizumab (loading dose of 500 mg given at Baseline and Week 2) or placebo by SC injection Q2W. Randomisation will be stratified by prior use of dupilumab, age (adolescent patients aged ≥ 12 to < 18 years will make up 12.5% of the overall population compared to adults aged ≥ 18 years), and baseline disease severity (IGA 3 versus 4).

Randomisation data will be kept strictly confidential, accessible only to authorised persons, until the time of unblinding of the allocated treatment of all trial patients after database lock. When the trial is completed and the data verified and locked, the randomisation codes will be made available for data analysis.

The Investigator or his/her delegate will contact the IWRS after confirming that the patient fulfils all the inclusion criteria and does not meet any of the exclusion criteria. The IWRS will assign a randomisation number to the patient, which will be used to link the patient to a treatment arm and will specify unique medication pack numbers for the first packages of trial treatment.

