4.1.2. Baseline and Double-Blinded Induction Period (week 0 to week 16)

At baseline visit (Day 1), patients who meet the study eligibility criteria will be 2:1 randomly assigned to their induction treatments with stratification based on previous use of dupilumab (Yes / No), age (adolescent patients ≤12 to <18 versus adults ≥18 years) and baseline disease severity (IGA 3/ IGA 4).

The treatment groups in the Blinded Induction Period are:

- Lebrikizumab 250 mg every 2 weeks (Q2W): 500 mg lebrikizumab administered at Baseline and Week 2 (loading dose)
- Placebo by Subcutaneous (SC) injection Q2W

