7.5. Adjustments for Covariates

Unless otherwise specified, the statistical analysis models for the Induction Period efficacy and health outcome analysis will include the following stratification factors for Baseline randomization: age (adolescent patients 12 to <18 versus adults ≥18 years) and baseline disease severity (IGA=3 versus IGA=4). Additionally, the following factors will be included in the models:

- Country of patient as recorded at screening
- For analyses of the full population (i.e. not the subgroups of dupilumab naïve or previously exposed patients), the stratification factor of prior use of dupilumab (yes/no) will be included.

If the model does not converge, country will be removed as a factor from the specific model.

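### The log-rank test for time-to-event endpoints names no strata, although randomisation is stratified and the hazard ratio beside it is adjusted

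*SAP*

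**What the plan says.** SAP section 9.4 sets out three steps for time-to-event endpoints.

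- Kaplan-Meier curves are produced.
- The arms are tested: "A comparison of the survival distribution curves for the 2 treatment groups will be made by means of the log-rank test". No strata are named.
- The effect is estimated: "The Cox proportional hazards model will be used to estimate the hazard ratio and its 95% CI of lebrikizumab compared with placebo". No p-value is asked of this model. Its content is given as "The main Cox proportional hazards model will include treatment group, with country, age, Baseline disease severity and previous exposure to dupilumab", all entered as factors.

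Protocol section 11.8.1.1 (part B) matches this. On allocation, Protocol section 9.6.2 says "Randomisation will be stratified by prior use of dupilumab, age", with baseline IGA (3 or 4) as the third factor. SAP section 4.1.2 agrees.

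SAP section 7.5 sets a general rule: "Unless otherwise specified, the statistical analysis models for the Induction Period efficacy and health outcome analysis will include the following stratification factors". It names age and IGA, and adds country and, for the full population, prior dupilumab. It does not say whether a log-rank test counts as a model.

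The endpoints concerned are time to TCS-free use (a listed secondary endpoint) and time to EASI 50, 75 and 90 (defined in SAP section 9.2). A second, whole-study time-to-event analysis follows the same paragraph.

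**The concern.** The CMH, MMRM and Cox analyses each list the randomisation factors explicitly. The log-rank test does not, so its plain reading is an unstratified two-group test.

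Two things follow. First, stratified randomisation holds the arms close to 2:1 within each stratum, so chance imbalance in those factors adds little to the real variability of the log-rank statistic. The unstratified variance does not credit this. If the factors predict the outcome, the variance is too large, the test rejects too seldom under the null, and power is lost. Second, the only p-value the plan names comes from an unadjusted comparison but will be read beside an adjusted hazard ratio and interval. At stake are some power and the coherence of the time-to-event tables.

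**Working it through.** **1. The plan's own power figures.** SAP section 4.3 gives 312 patients (208 and 104), two-sided 5%. With pooled response rate p̄, power = Φ[(Δ − 1.96·SE₀)/SE₁], where SE₀ = √[p̄(1−p̄)(1/104 + 1/208)] and SE₁ = √[p₁(1−p₁)/104 + p₂(1−p₂)/208].

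- EASI 75, 30% v 55%: p̄ = 0.467, SE₀ = 0.0599, SE₁ = 0.0566, power 0.990.
- IGA 0/1, 12% v 30%: p̄ = 0.24, SE₀ = 0.0513, SE₁ = 0.0450, power 0.961.
- Pruritus NRS, 9% v 43%: power above 0.999.
- Product under independence: 0.952.

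The stated bounds (above 95% and above 90%) reproduce. No event count, hazard ratio or power is given for any time-to-event endpoint, so the next step rests on assumptions.

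**2. Simulation.**

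- From the documents: N = 312, 2:1, eight strata, 60 prior-dupilumab patients (the cap) and 39 adolescents (12.5%).
- Assumed: permuted blocks of 6 within strata; 40% with IGA 4; 10% censored early; continuous event times; placebo event probability by Week 16 in the reference stratum of 35% or 70%.
- Assumed prognostic hazard ratios (IGA 4 / prior dupilumab / adolescent): none 1/1/1; modest 0.75/0.8/1.1; strong 0.5/0.6/1.3; very strong 0.3/0.4/1.5.

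With U = Σ(observed − expected events on lebrikizumab) and V = Σp(1−p), where p is the lebrikizumab share of those at risk at each event, the unstratified test is Z = U/√V. The stratified test is Z = ΣUₛ/√ΣVₛ over the eight strata. Both reject at |Z| > 1.96.

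| Event prob. | Treatment HR | Factors | Runs | Unstratified | Stratified | Gain (points) |
|---|---|---|---|---|---|---|
| 35% | 1 | none | 20,000 | 0.049 | 0.050 | – |
| 35% | 1 | modest | 20,000 | 0.048 | 0.049 | – |
| 35% | 1 | strong | 20,000 | 0.048 | 0.052 | – |
| 35% | 1 | very strong | 20,000 | 0.037 | 0.047 | – |
| 70% | 1 | strong | 20,000 | 0.039 | 0.049 | – |
| 70% | 1 | very strong | 20,000 | 0.032 | 0.050 | – |
| 35% | 1.5 | none | 1,500 | 0.547 | 0.543 | −0.4 |
| 35% | 1.5 | modest | 700 | 0.511 | 0.507 | −0.4 |
| 35% | 1.5 | strong | 700 | 0.430 | 0.456 | 2.6 |
| 35% | 1.5 | very strong | 700 | 0.386 | 0.426 | 4.0 |
| 35% | 1.8 | strong | 700 | 0.780 | 0.799 | 1.9 |
| 70% | 1.4 | strong | 8,000 | 0.519 | 0.564 | 4.4 |
| 70% | 1.4 | very strong | 8,000 | 0.400 | 0.515 | 11.4 |

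Rows with HR 1 are type I error; the others are power. Gains were computed before rounding. The Monte Carlo standard error of a single rate is about √(0.05×0.95/20,000) = 0.0015 for the first six rows and √(0.43×0.57/700) = 0.019 for the 700-run rows. Both tests were run on the same simulated trials, so the differences are better determined than that, but the 700-run gains remain approximate.

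**3. Second simulation, with event times grouped to Weeks 2, 4, 8, 12 and 16** (4,000 trials per setting, 35% placebo events). With moderate factors (hazard ratios 0.6/1.3/0.7), type I error was 4.4% unstratified v 4.8% stratified, and power at HR 1.6 was 61.6% v 62.7%. With strong factors (0.35/1.5/0.5), type I error was 4.6% v 5.2%; power was 51.6% v 56.2% at HR 1.6 and 74.4% v 78.0% at HR 1.8. The pattern is the same.

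**4. Which event rate is relevant?** The plan's EASI 75 rates imply (208×0.55 + 104×0.30)/312 = 145.6/312, or 47% pooled at Week 16. The power simulations averaged 90 to 129 events at 35% and 172 to 196 at 70%, so about 146 lies between them. Intercurrent-event handling aside, first reaching EASI 75 at any visit is at least as frequent as having it at Week 16.

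**5. Log-rank p-value v Cox interval.** The unstratified log-rank test and a Cox model adjusted for the three factors (country not simulated) disagreed on 5% significance in 1.8% (none), 1.4% (modest), 3.7% (strong) and 4.3% (very strong) of trials at HR 1.5, and in 3.4% (strong) at HR 1.8. With strong factors at HR 1.5, only the Cox result was significant in 3.0 of the 3.7 points.

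**6. Sparse cells.** If the factors are independent, 60 × 0.125 = 7.5 patients are both adolescent and previously on dupilumab. At 40% IGA 4 that is 4.5 and 3.0 per cell, with 1.5 and 1.0 on placebo. Adding about 9 countries gives 8 × 9 = 72 cells, averaging 312/72 = 4.3 patients each.

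**The case against.** The strongest defence is that the pairing is deliberate and coherent: an unadjusted test for unadjusted Kaplan-Meier curves, and an adjusted model for the effect size. The word unstratified appears nowhere, and SAP section 7.5 might be read as bringing the factors in. No prognostic effect is documented, and with null or modest factors the two tests are indistinguishable. Stratifying creates a few very small cells. The endpoints do not decide the trial: SAP section 7.9 rests success on the primary endpoint alone.

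Most of this stands and limits the point. It does not remove it. Section 7.5 speaks only of models in the Induction Period, so at best it leaves two programmers free to produce different p-values. The sparse cells cost almost nothing: with factors of no prognostic value, power was 0.543 stratified against 0.547.

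Three stronger readings are tempting, and none is supported.

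- A reader might infer that the planned test is invalid. It is not: type I error is at or below 5%, never inflated.
- A reader might take the conservatism as established. It depends on prognostic strength that the documents do not give.
- A reader might expect stratification alone to make the p-value match the hazard ratio. It would not, because the Cox model also contains country and enters the factors as covariates rather than strata.

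**Conclusion.** The point holds as a low-cost improvement. As written, the log-rank test is unstratified on its plain reading, and it is valid. Compared with a test stratified by the randomisation factors, it loses nothing material if those factors are weak or modest, and about 2 to 11 points of power if they are strong or very strong. The top of that range needs very strong factors and a 70% event probability together. The unadjusted p-value and the adjusted interval can point different ways, in about 1% to 4% of simulated trials.

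These sizes rest on the assumed prognostic hazard ratios, event probabilities, IGA split and censoring. Neither simulation modelled time to TCS-free use from TCS records, so the sizes carry over to that endpoint only by analogy. SAP section 9.6 labels time to TCS-free days as key secondary, but the endpoint tables mark only IGA 0/1 and pruritus NRS as such. No confirmatory conclusion is affected.

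**What to change.** In SAP section 9.4:

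- State that the log-rank test is stratified by age group, baseline IGA and, in the overall population only, prior dupilumab. Leave country out because of sparse cells.
- Report the treatment p-value from the adjusted Cox model beside its hazard ratio and interval, and label which p-value belongs to which analysis.
- Say whether the same applies to the whole-study time-to-event analysis, which SAP section 7.5 does not cover.

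The cost is a sentence or two, one STRATA specification and one extra table entry, to be settled before unblinding. The downside is a few small strata, and no gain if the factors turn out not to be prognostic.
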